#### 12.6 Table 6 Actions for Postoperative Withdrawal

Table 6 Actions for Postoperative Withdrawal					
Example	Actions	Follow -up			
Subject	Document Subject's request for withdrawal from				
withdraws	

the study in the source

Complete End of Study/Withdrawal eCRF

	Do not continue			
consent	Update Screen/Enrollment Log				
	Document in source				
D 41	Complete Adverse Event eCRF	Do not			
Death	Complete End of Study/Withdrawal eCRF	continue			
	Update Screen/Enrollment Log				
	See Section 14.5, Table 9 Revisions and	Do not continue if the			
Revision	Reoperations	femoral stem has been			
	Acopei ations	removed or revised.			

CONFIDENTIAL Page 26 of 53
Version Date: May 7, 2018

DePuy Synthes / Actis® Total Hip System
Protocol #14014 / Version B

	Please continue to follow
	if the femoral component
	has not been removed or
	revised

#### 13 ADVERSE EVENTS (AES)

An adverse event (AE) is defined as an untoward medical occurrence, unintended disease or injury, or untoward clinical signs (or change or worsening of a pre-existing medical condition) in a patient, which may or may not have an association with the device. In addition, an adverse device effect is defined as "any untoward and unintended response to a medical device". Further types of AEs and definitions are in **Table 7** below. AEs are reported beginning from when the informed consent is signed until Subject participation has ended (study completed or consent withdrawn. This protocol requires each site to report AEs to their respective IRB/REC, EC, per their IRB/REB/EC's respective requirements. Device related AEs will be reviewed by DePuy Synthes and reported, if applicable, to the appropriate regulatory body.

Study Sites have two (2) weeks from when they become aware of device and /or procedure related AEs to inform the Sponsor via the AE eCRF.

For this study, only the AEs related to the study devices (excluding the Patient Activity Tracking devices) or the procedure are to be reported (please refer to Figure 13.1). The determination whether the AE was related to the device or procedure will be based upon whether a causal relationship between the device or procedure and the AE is at least a reasonable possibility, *i.e.*, the relationship cannot be ruled out. A causal relationship cannot be ruled out if, in the medical judgment of the Investigator, the effect follows a reasonable temporal association with the use of the device and/or is confirmed by the improvement of the effect upon discontinuation of the clinical use of the device, and/or the effect is not reasonably explained by the Subject's clinical state.

A record of each device or procedure related AE, including details of the nature, onset, duration, severity, relationship to the device, relationship to the operative procedure and outcome, will be made on an AE eCRF. Subjects must be questioned about any new or changed AEs at each subsequent follow-up visit, whether scheduled or not.

AEs must be followed to resolution, or end of subject's study participation. When a Subject ends participation in the trial, all open AE outcomes must be designated in the AE eCRF as either "Recovered/Resolved with no residual effects", "Recovered/Resolved with residual effects", "Ongoing", "Death", or "Unknown" providing a resolution date (if applicable) or ongoing designation.

CONFIDENTIAL Page 27 of 53
Version Date: May 7, 2018

[figure not shown]
DePuy Synthes / Actis® Total Hip System
Protocol #14014 / Version B

There is no personal benefit to the Subject for participation in this study. However, data collected in this study will contribute to the safety profile of the Actis® Total Hip System.

**Figure 13.1**: AE Reporting flowchart illustrates a series of question a site must consider when determining whether a given clinical observation must be reported and which AEs do not need to be reported for this study.

CONFIDENTIAL Page 28 of 53
Version Date: May 7, 2018

DePuy Synthes / Actis® Total Hip System
Protocol #14014 / Version B

Adverse Events (AEs) occurring postoperatively after hip arthroplasty are not unique to the Actis® Total Hip System and are like those that may occur with any THA or hemi-hip arthroplasty. And, per

CONFIDENTIAL Page 29 of 53 Version Date: May 7, 2018 DePuy Synthes / Actis® Total Hip System Protocol #14014 / Version B the Instructions for Use (IFU), which is included in the implant packaging, the following are generally the most frequently encountered AEs and complications in hip arthroplasty.

#### General:

- 1. Change in position of the prosthetic components, often related to the factors listed in WARNINGS AND PRECAUTIONS.
- 2. Early or late loosening of the prosthetic components, often related to factors listed in WARNINGS AND PRECAUTIONS.
- 3. Fatigue fracture of the femoral stem, often related to factors listed in WARNINGS AND PRECAUTIONS.
- 4. Excessive wear or fracture of the bearing components due to: intra-operative damage to the prosthetic components, loose cement, bone fragments, metallic particles, ceramic particles or other factors listed in the WARNINGS AND PRECAUTIONS.
- 5. Early or late infection.
- 6. Peripheral neuropathies, Subclinical nerve damage may also occur as a result of surgical trauma.
- 7. Tissue reactions, osteolysis, and/or implant loosening caused by metallic corrosion, allergic reactions, wear or particulate debris (such as loose cement, metallic, polyethylene or ceramic particles).

#### **Intra-operative:**

- 1. Acetabular perforation.
- 2. Femoral shaft perforation, fissure, or fracture, which may require the use of internal fixation.
- 3. Trochanteric fracture.
- 4. Damage to blood vessels (e.g., iliac, obturator and femoral artery).
- 5. Temporary or permanent nerve damage (e.g., femoral, obturator or isolated peroneal nerve).
- 6. Subluxation or dislocation of the hip joint due to implant size or configuration selection, positioning of components and/or muscle and fibrous tissue laxity.
- 7. Breakage or chipping of the ceramic femoral head.
- 8. Lengthening or shortening of the affected extremity.

CONFIDENTIAL Page 30 of 53
Version Date: May 7, 2018

DePuy Synthes / Actis® Total Hip System
Protocol #14014 / Version B

#### **Early Postoperative:**

- 1. Cardiovascular disorders including venous thrombosis, pulmonary embolism and myocardial infarction.
- 2. Hematoma and/or delayed wound healing.
- 3. Pneumonia and/or atelectasis.
- 4. Subluxation or dislocation.

#### Late Postoperative:

- 1. Trochanteric avulsion from excessive muscular tension, weight-bearing, or inadvertent intraoperative weakening of the trochanter.
- 2. Aggravation of problems in the ipsilateral or contralateral knee and ankle joints due to leg length discrepancy, femoral medicalization and/or muscular deficiencies.
- 3. Femoral or acetabular fracture due to trauma or excessive loading, particularly in the presence of poor bone stock caused by sever osteoporosis, bone defects from previous surgery, reaming procedures, or bone resorption.
- 4. Bone resorption which may contribute to the deterioration of fixation and eventual loosening of the implant.
- 5. Peri-articular calcification or ossification which may lead to a decrease in joint mobility and range of motion.
- 6. Traumatic arthrosis of the ipsilateral knee secondary to intra-operative positioning, of het extremity during surgery.
- 7. Subluxation or dislocation.

The incidence and severity of complications in hip replacement are usually greater in revisions than in primary operations. Common problems encountered in revision surgery may include difficulty in placement of the incision, removal of ectopic bone and old bone cement, positioning and fixation of components, and/or obtaining adequate bony support. In general, increased operative time, blood loss and risk of infection, pulmonary embolus and wound hematoma can be expected with revision procedures.

**WARNING:** if postoperative breakage or chipping of the ceramic femoral head component is confirmed, surgery for its removal must be performed as soon as reasonably possible.

CONFIDENTIAL Page 31 of 53
Version Date: May 7, 2018

DePuy Synthes / Actis® Total Hip System
Protocol #14014 / Version B

# 13.1 Table 7 Definitions of Adverse Event (AE) Types, Device Deficiency.

For this protocol, the term "expected" will be synonymous with the term "anticipated" and "unexpected" will be synonymous with "unanticipated".

Table 7 Definitions of Adv	verse Event (AE) Types, Device Deficiency	
Awareness (Date of AE Awareness)	The day, month and year that the study site becomes	
121142 011000 (2 400 01 122 121142 011000)	aware of information from any source that reasonably	
	suggests that an AE has occurred.	
	Note: This date may or may not correspond to the date of	
	onset. The date of awareness is critical to reporting	
Administration of the control of the	timelines.	
Adverse Event (AE)	AE is defined as an untoward medical occurrence, unintended disease or injury, or untoward clinical signs	
	(or change or worsening of a pre-existing medical	
	condition) in a patient, which may or may not have an	
	association with the device. AE is synonymous with	
	"complication" or "medical event".	
Adverse Device Effect (ADE)	ADE is defined as an Adverse Event related to the use of	
	an investigational medical device.	
	Notes: This definition includes adverse events resulting	
	Notes: This definition includes adverse events resulting from insufficient or inadequate instruction for use,	
	deployment, implantation, installation or operation, or	
	any malfunction of the medical device under study. This	
	definition includes any event resulting from user error or	
	from intentional misuse of the medical device under	
Cardana Adama Darda Effect (CADE)	study).  SADE is defined as an Adverse Device Effect that has	
Serious Adverse Device Effect (SADE)	resulted in any of the consequences characteristic of a	
	serious adverse event.	
Serious Adverse Event (SAE)	SAE is defined as an Adverse event that:	
	• led to a death,	
	• led to a serious deterioration in the health of the	
	Subject that either:	
	o resulted in a life-threatening illness or injury,	
	or resulted in a life-threatening illness or injury,	
	OI	
	o resulted in a permanent impairment of a body	
	structure or a body function, or	
	•	

CONFIDENTIAL Page 32 of 53

Version Date: May 7, 2018

DePuy Synthes / Actis® Total Hip System Protocol #14014 / Version B

- o required inpatient hospitalization or prolongation of existing hospitalization, or
- resulted in medical or surgical intervention to prevent life threatening illness or injury or permanent impairment to a body structure or a body function.
- led to fetal distress, fetal death or a congenital abnormality or birth defect.
- Other serious important medical events. Report when the event does not fit the other outcomes, but the event may jeopardize the patient and may require medical or surgical intervention (treatment) to prevent one of the other outcomes.

Examples of procedure related serious AEs (SAEs) may include: stiffness requiring manipulation of the hip under anesthesia, dislocation of hip requiring closed reduction, Deep Vein Thrombosis (DVT) without hospitalization. Examples of device related SAEs may include radiolucent lines around the femoral component or device dislocation.

# **Unexpected/Unanticipated Adverse Device Effect (UADE)**

Is defined as any serious adverse effect on health or safety, or any life-threatening problems, or death, caused by, or associated with, a device, if that effect, problem, or death was not previously identified in nature, severity, or degree of incidence in the Clinical Investigation Plan, or application, or any other unanticipated serious problem associate with a device that relates to the rights, safety, or welfare of Subjects. A UADE will not be listed in the Instructions for Use (IFU).

All potential UADEs that occur during this investigation must be reported by the Investigator no later than 72 hours from the time when the Investigator is aware of the event to the Sponsor by [contact], electronic correspondence, or [contact].

CONFIDENTIAL Page 33 of 53

Version Date: May 7, 2018

DePuy Synthes / Actis® Total Hip System Protocol #14014 / Version B

	In the event of a UADE or serious adverse device effect,
	the Investigator should institute appropriate therapeutic
	and follow-up measures in accordance with good
	medical practice and notify the local IRB/REB/EC. The
	Investigator must document follow-up treatment in the
	"comment" section of the AE eCRF. A full written report
	of the event must be forwarded to DePuy Synthes within
	10 working days of the discovery.
	DePuy Synthes must notify FDA, all reviewing
	IRB/REB/EC's and all participating Clinical
	Investigators of all UADEs within 10 working days of
	first receiving notice of the event. In addition, the event
	will be reported to the DePuy Synthes Complaint
	Handling Unit (CHU) for investigation.
Device Deficiencies	Are defined as in adequacy of a medical device with
	respect to its identity, quality, durability, reliability safety
	or performance. Device deficiencies include
	malfunctions, use errors and inadequate labeling. Device
	deficiencies should institute appropriate therapeutic and
	follow-up measures in accordance with good medical
	practice and notify the IRB/REB/EC as applicable. The
	Investigator must document follow-up treatment of the
	AE and the Sponsor will report the event to the DePuy
	Synthes Complaint Handling Unit for investigation.

#### **13.2 Definition of AE Severity**

An adverse event (AE) or an adverse device effect (ADE) may be:

- **Mild**: Easily tolerated and transient in nature with minimal or no impairment of normal activity. Intervention is not indicated. Clinical or diagnostic observations only and no impairment of normal activity.
- **Moderate**: Poorly tolerated, sustained and interferes with normal activity and requires medical attention. Intervention is either noninvasive or not indicated. Activities of daily living can be sustained.
- **Severe**: Poorly tolerated, requires intervention and significantly affects activities of daily life; or places the Subject at immediate risk or harm.

CONFIDENTIAL Page 34 of 53
Version Date: May 7, 2018

DePuy Synthes / Actis® Total Hip System
Protocol #14014 / Version B

# 14 DETERMINATION OF RELATIONSHIP TO DEVICE AND/OR PROCEDURE AND ADES AND SADES

#### 14.1 Device or Procedure Related

As noted in **Section 13**, for this study, only the AEs related to the study devices or the procedure are to be reported and the determination of whether the AE is related to the device or procedure is based on the definition provided in that section.

Relationship to study device or procedure should both be rated as follows: "Definitely", "Probably", "Possibly", "Remote Possibility", or "Definitely not".

Table 8 Definitions of Device-Relatedness and Procedure-Relatedness for AEs	
Term	Description
Definitely	The relationship between study device or procedure and event does
	exist and is confirmed upon further investigation by the
	Investigator
Probably	The relationship between study device or procedure may exist if
	other causes are unlikely
Possibly	The relationship between study device or procedure could exist;
	however, other causes are possible
Remote Possibility	There is minimal chance that a relationship exists between the
	study device and/or procedure
Definitely Not	There is definitely no relationship between study device or
	procedure and the event

#### 14.2 Worsening Adverse Events

For a worsening AE, resolve the original AE on an AE eCRF and complete an additional AE eCRF for the new Severity. Examples of this exercise will be included in the eCRF Completion Instructions (CCIs), a tool which will be provided to site to help aid in entering data into the EDC system. A simple example is that if a Subject has a superficial wound infection with oral medication as a treatment that progresses to a deep wound infection with additional treatment (*e.g.*, inpatient hospitalization for an irrigation and debridement). The study site must resolve the superficial wound infection and report the worsening on an additional AE eCRF. Each AE will be counted individually – as in one superficial wound infection and one deep wound infection AE/SAE.

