Primary, Secondary and Tertiary Endpoints:	
 
Primary endpoint:     Harris Hip Score at minimum 2-years postoperatively.
 
Secondary endpoints: 
 
Harris Hip score at 3-months and 1-year
 
Radiographic evaluation at 2-years postoperatively, inclusive of leg length discrepancy
 
Type and frequency of device and procedure related AEs through 2-years postoperatively
 
Device survivorship at 2-years postoperatively
 
 
 
Tertiary endpoints: 
 
Change in Subject Outcomes (i.e., FJS-12, HOOS and Subject Hip Evaluation) will be measured and compared from preoperative to 6-weeks, 3-months, minimum 1-year and minimum 2-years.
 
Study Sites will be given the opportunity to participate in a non-required parallel activity (to collect tertiary outcomes) of this study, specifically, "Patient Activity Tracking".
 
At the participating study sites, Subjects choosing to participate in Patient Activity Tracking will wear a device that looks somewhat like a wrist watch. The Patient Activity Tracking device will link via a downloaded mobile application (app) (i.e., ActiTrakTM) to the Subject's smartphone (i.e., iPhone or Android phone) or to a Sponsor provided Android tablet. Any Sponsor provided Android tablet will be for study use only in order to provide pre-populated passive and actively reported Subject activities such as Pain, Location of Pain, Mood/Emotion, Activities of Daily Living, and Range of Motion from the time of consent preoperatively through 3 months postoperatively. After surgery, there will be question about Subject Satisfaction periodically. Any Sponsor provided Android tablet will be returned to the Sponsor at the 3-month follow-up interval or at any premature study termination after consent and enrollment.
 
 
 
	

Table 2 Study Summary	
Title:	Actis® Total Hip System 2-Year Follow-up
Procedure Schedule:	Subjects will be seen at the following intervals: preoperative, operative, 6-weeks, 3-months, minimum 1-year, and minimum 2-years postoperatively.
Safety:	Only device or procedure related adverse events (AEs) for enrolled Subjects are to be reported.

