eCRF AE	eCRF. Only one AE can be recorded on an AE eCRF.			
	An AE can be defined as Mild, Moderate or Severe and these terms are			
	defined in Section 13 (The definitions of Serious Adverse Event and			
	Unexpected Adverse Device Event or UADE are defined in Section 13 ).			
	Early responsible AE places resolve the previous AE on aCDE and remort			
	For a worsening AE, please resolve the previous AE on eCRF and report			
Dations Assisting	a "New" AE eCRF for the new Severity.			
Patient Activity	The Patient Activity Tracking device is a wearable watch-like device that			
Tracking (ActiTrak TM )	will be linked with the ActiTrack TM app that is downloaded on to a Subject's own smartphone (iPhone or Android phone, or Sponsor provided			
(ACHITAK )	Android tablet) and will be used at some sites. It is not mandatory for a			
eCRF PA	study site or a study Subject to participate. For details on the Patient			
CRITA	Activity Tracking device (i.e., the wearable watch-like device) and the			
	required downloaded mobile app, refer to Appendix G .			
	required do winouaca moone upp, terer to rependix G.			
	Preoperatively at from the time of consent through 3 months			
	postoperatively is the preferred timeline for participation.			
	Data collected via the Patient Activity Tracking is a part of the tertiary			
	endpoints (Section 16).			
End of Study/	Please complete the End of Study eCRF when a study Subject has either			
Withdrawal	completed the study primary endpoint (2-year follow-up) or for any reason			
	for withdrawal; some examples are listed below:			
eCRF DS	Withdrawal of consent			
	Investigator decision			
	• Death (correlate with AE eCRF)			
	Lost to follow-up			
	General screen failure (includes intra-operative screen failures)			
	Study site withdrew/terminated from study			
	Adverse event related (including revisions postoperative, correlate)			
	with AE eCRF)			
	• Other reasons – specify			
	Revision (correlate with AE eCRF)			
	Completion of final endpoint at minimum 2 years			

CONFIDENTIAL Page 24 of 53
Version Date: May 7, 2018

DePuy Synthes / Actis® Total Hip System
Protocol #14014 / Version B

NOTE: AE eCRF will be completed for only device and procedure related AEs. For further details and directions regarding revision of any study component please also refer to Table 8 Revisions and Reoperations.

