- Radiographic measurements will provide True LLD by measuring each leg to the nearest millimeter. A LLD of 3 cm or greater will be considered a true LLD. A McNemar's test of discordant pairs will be utilized to compare perceived vs. actual LLD before surgery, and also to compare perceived vs. actual LLD after surgery.
- o Analysis of Change (post-surgical pre- surgical) of True LLD: Compare the difference between the absolute true LLD before and after hip replacement surgery for those cases that had a true LLD prior to hip replacement surgery (using a definition of 3 cm or greater as the threshold). The analysis variable will be the absolute value of the difference between the right and left knee and a paired t-test will be used to assess this difference.
- Analysis of proportion of cases that have true LLD after surgery will be presented and this
  will be compared to the proportion that had true LLD prior to surgery; McNemar's test of
  discordant pairs will be conducted.
- The type and frequency of AEs through 2 years post-operatively will be presented in table form and via a listing. Frequencies and listing of AE's seriousness, severity, whether unanticipated, outcome, and treatment will also be presented.
- Device survivorship at 2 years post-operatively. Kaplan-Meier survivorship will be conducted with removal of any component, defined as revision, for any reason specifying the event of interest. Cases not revised will be censored at their date of last follow-up, death, or withdrawal from the study. Survivorship point estimates and 95% confidence intervals will be presented when 40 subjects are left being followed. Survivorship analysis is not planned for the cohort of hemi-hip subjects as the sample size is insufficient; however, a listing will be provided to present all subjects requiring removal of any component.
- Stem Revision at 2 years post-operatively.

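### A worsened adverse event is closed and counted again with no rule for combining the two records, and no device-related adverse event rate is explicitly planned

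*Combined protocol and SAP*

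**What the plan says.** **Worsening.** Section 14.2 instructs: "For a worsening AE, resolve the original AE on an AE eCRF and complete an additional AE eCRF for the new Severity". It then states that "Each AE will be counted individually", and illustrates this with a superficial wound infection that becomes deep and so makes two events. Table 4 (Section 12.2) repeats the instruction to sites: "For a worsening AE, please resolve the previous AE on eCRF and report" a new form at the new severity.

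**Outcome codes.** Section 13 offers "Recovered/Resolved with no residual effects", a second resolved code with residual effects, and codes for ongoing, death and unknown. It introduces the list for events still open when a subject leaves the study.

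**Planned summaries.** Section 16.12 plans type and frequency of events in a table and a listing, and then: "Frequencies and listing of AE's seriousness, severity, whether unanticipated, outcome, and treatment will also be presented". Section 16.10 gives the general rule that categorical variables are summarised by count and percentage of subjects. Section 16.8 assigns adverse events to the Safety Set.

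**Relatedness.** Section 13 has the relationship to the device and the relationship to the procedure recorded for each event. Under Section 14.1, relationship to the device or "procedure should both be rated as follows", on five levels from Definitely to Definitely Not. Table 2 (Section 4) words the secondary endpoint as "Type and frequency of device and procedure related AEs through 2-years postoperatively".

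**The concern.** A site that follows Section 14.2 closes the first record at the moment the event gets worse. None of the listed outcome codes describes that closure, and the instruction itself is to resolve, so in practice the first record takes a resolved code. An episode that has not resolved then enters the outcome table as resolved, and enters the severity table twice, once at its milder grade. No text available links the two records or says which severity and outcome represent the episode or the subject.

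Relatedness is a separate gap. The Section 16.12 list of attributes does not include it, so device-related and procedure-related events are summarised together unless someone adds a split later.

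Adverse event type and frequency is a secondary endpoint, and safety of this device is a stated purpose (Section 8). In an uncontrolled study, a counting unit or relatedness cut-off chosen after the data are seen is hard to defend.

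**Working it through.** **Figures to reproduce.** The documents state no adverse event rate, event count or worsening rate, so there is no adverse event figure to reproduce. The only computed design figure, the 1.4-point margin on the Harris Hip Score in Section 16.9, does reproduce (1.96 × 10 / √200 = 1.386), but has no bearing here.

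**One episode traced through the rule.** Take a moderate event that becomes severe and is ongoing at exit (grades and outcome assumed).

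- As one episode: 1 event, severe, ongoing.
- As records: 2 events, one moderate and resolved, one severe and ongoing.
- As subjects: 1 subject with any event and 1 with any severe event, under either method.

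**General form.** Let there be E episodes, of which a share w worsens once. Let r be the share of episodes whose final outcome is resolved, and s the share whose worst grade is severe. Assume that each first record is coded resolved, and that worsened episodes start below severe and end severe. Then:

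- Records = E(1 + w)
- Record-level resolved share = (r + w)/(1 + w), a shift of +w(1 − r)/(1 + w)
- Record-level severe share = s/(1 + w), a shift of −sw/(1 + w)

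**Results per 100 episodes.** The values of w, r and s are assumptions.

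| w | Records | Resolved, r = 60% | Resolved, r = 80% | Severe, s = 20% |
|---|---|---|---|---|
| 2% | 102 | 60.8% | 80.4% | 19.6% |
| 5% | 105 | 61.9% | 81.0% | 19.0% |
| 10% | 110 | 63.6% | 81.8% | 18.2% |
| 20% | 120 | 66.7% | 83.3% | 16.7% |

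At w = 20%, for example, resolved is (60 + 20)/120 = 66.7%, and severe is 20/120 = 16.7%. The number of severe records stays at 20; the total and the shares move. The resolved shift shrinks as r rises and is zero at r = 100%.

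**Relatedness, passages side by side.** Section 13 collects both relationships and Section 14.1 grades each on five levels. Section 16.12 names seriousness, severity, unanticipated status, outcome and treatment. Relationship is absent from that list, and no analysis cut-off on the five levels is stated.

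**The case against.** The strongest reply is that Section 16.10 summarises categorical variables by subject. This stands for subjects with any event and with any severe event, which the rule cannot change. It does not settle the severity and outcome summaries: a subject with a worsened event has two grades and possibly two outcomes, and nothing says which applies. Section 14.2 also states that events are counted individually, which points to record counts, so the unit is unsettled.

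Superficial and then deep infection can fairly be defended as two event types, and for a type-and-frequency endpoint both belong in the type table. That stands too. But the rule is triggered by any change in severity, including one event that merely becomes more severe.

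The case report forms (Appendix A) and the completion instructions are not in the documents available. They might link the records or offer another code, and the Section 13 list is framed for events open at exit. The point therefore rests on the text that can be read.

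On relatedness, Table 7 lists adverse device effects among its event types, so a table by type might be read as including them. Section 16.12 does not say so, and the Table 7 definition gives no cut-off on the five-level scale. It is also unclear whether events rated Remote Possibility pass the reporting criterion in Section 13, and the reporting flowchart is not shown.

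Two stronger readings are tempting. A reader might infer that device-related figures are distorted. They are not: none is explicitly planned, and the ratings needed to produce one are collected. A reader might also infer a large bias from an example such as 10 episodes with 3 worsening and ongoing at exit, where resolved reads 10/13 (77%) against 7/10 (70%). That assumes 30% worsening, which nothing in the documents supports.

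**Conclusion.** The point holds for record-level figures. As written, the rule inflates the event count by the factor 1 + w, tilts outcomes towards resolved unless every episode finally resolves, and lowers the severe share when events worsen to severe. At an assumed worsening rate of 2% to 20%, the shifts are about +0.8 to +6.7 points from 60% resolved and −0.4 to −3.3 points from 20% severe. The true size is unknown. These results assume that the first record is coded resolved and that the unseen forms and instructions contain no link between records.

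At subject level, what remains is a missing rule for the severity and outcome of a subject with linked records. The relatedness point is an omission from the planned summaries. Both are worth correcting before analysis, since the decisions are cheap to make in advance.

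**What to change.** Amend Section 16.12; no form change is needed.

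1. Derive a link between each worsened event and its successor record.
2. Summarise severity and outcome per linked episode and per subject, at worst severity and final outcome. Do not count a record closed by worsening as resolved.
3. Keep both records in the listing and in the event-type count.
4. Tabulate number and percentage of subjects, with exact 95% confidence intervals, separately for device-related and procedure-related events. State the cut-off on the five-level scale in advance, and add a sensitivity version that includes Remote Possibility.

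The cost is minor programming and two extra tables. A new outcome code on the form is unnecessary, and would be awkward: Section 10.6 records that the 225 total hip subjects had been reached by June 5, 2017, before this version of May 7, 2018, so existing records would need recoding.
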